If children are eligible and assent and consent are provided, remaining baseline assessment measures are administered (see Table 4) and participants are randomized. Randomization procedures occur prior to the screenings by the local PC and Drs. [name] and [name], reducing any randomization bias. Interviewers have a numbered stack of consent forms that are used in numerical order. Each consent form includes an attached envelope with randomization status (see Human Subjects for more information). Guardian-child dyads randomized to TF-CBT begin the 12-week group protocol within 2 weeks. All dyads are assessed again at 12-14 weeks post-baseline, 6-months, and 12-months post baseline. For all assessment meetings, children and guardians receive a small incentive for participation costing <\$2.50, (e.g., bag of sugar, laundry soap, pen).

Table 4. Study Measures (All Measures are included in Appendix A)

Domain; Respondent ^A	Measures & Indicators	Interval [*]	
Demo-graphics; G	Demographic Survey. We assess pertinent demographic information (e.g., guardian characteristics, years caring for child, home situation) using an established demographics measure from POFO, also used in the feasibility study. † +	BL, 12w, 6M, 12M	
Clinical Outcomes	Posttraumatic Stress; C, G	UCLA PTSD Index for DSM-IV¹⁰⁸ (UCLA PTSD-RI). The 38-item UCLA PTSD RI assesses trauma exposure and PTS symptoms. Response choices for PTS items are 0 - 4. The UCLA PTSD RI demonstrates good convergent validity and good to excellent test-retest reliability. Cronbach’s α in the range of .90. †	BL, 12w, 6M, 12M
	Behavioral Difficulties; G	Strengths & Difficulties Questionnaire¹⁰⁷ (SDQ). The SDQ is a brief behavioral screening survey (ages 3-16) with 25 items on 5 scales (Emotional Symptoms, Conduct Problems, Hyperactivity/Inattention, Peer Relationship Problems, & Prosocial Behavior). Response choices are from 0-2. The SDQ has been shown to have good discriminant validity and acceptable levels of test-retest reliability ¹⁰⁸ and a Cronbach’s α of .73 ¹⁰⁹ . †	BL, 12w, 6M, 12M
	Childhood Traumatic Grief, C	The UCLA Trauma Psychiatry Service Grief Inventory , (TPSG) is a 10-item measure that includes a subset of the items on the Expanded Grief Inventory ¹¹⁰ and is used to assess CTG symptoms. The scale has demonstrated moderate - high levels of internal validity, and has been used successfully with children aged 6 and older. †	BL, 12w, 6M, 12M

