To test how TF-CBT influences trajectories of symptoms over time (e.g., 6-months, 12-months), analyses may be expanded to incorporate multiple times of assessments by adding a third level to the above model to test a growth curve model in the MLM framework. Because there are expected to be no differences across conditions at pre-treatment, the intercept could be fixed to the final time point (12-months), allowing two related but distinct questions to be tested: (1) does TF-CBT predict lower levels of symptoms at 12-months; and (2) does TF-CBT produce greater changes (reductions) in symptoms over time than receipt of usual care? The general Level 1 equation would then represent an individual's level of symptoms at a given time point, Level 2 equation would represent individual differences in the Level 1 equation, and Level 3 would represent group differences in the Level 2 equations. Thus the new Level 1 equation would be: $Symptoms_{itg} = B_{0ig} + B_{1ig}Time + e_{itg}$, representing Symptoms at time t for individual i in group g , B_{0ig} being the level of symptoms at Time 0, and B_{1ig} being the effects of Time on symptoms (i.e. the rate of change in symptoms over time). Both the intercept and slope would be allowed to randomly vary across individuals, allowing their prediction from individual level variables (such as pre-treatment symptoms or covariates). For example, the Level 2 equation for the effects of Time would be $B_{1ig} = \pi_{00} + \pi_{01}Cov + r_{00}$. Finally, effects at Level 2 would also be allowed to randomly vary across groups, allowing us to model the effects of condition on the level of symptoms at the final time point, and on the rate of change over time.

It may be that there are significant individual differences in symptoms at 12-weeks, but that these differences do not continue to increase or are not maintained. The hypothesis of decreasing gains for the TF-CBT condition would be tested by adding a quadratic component to the linear growth model. Specifically, the quadratic effect (of time, represented as $time^2$) would test whether there are decelerations in the rate of change in symptoms from baseline to the 12 month outcome, and whether there are individual differences in those decelerations.

Aim 2. Examine any differences in clinical or implementation outcomes for country (TZ; KE) or setting (urban, rural), including differences in receipt of usual care.

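### The time-squared term tests whether the TF-CBT effect levels off, not whether it is lost, and no stated test estimates change since 12 weeks

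*Combined protocol and SAP*

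**What the plan says.** Section 3C5b, Aim 1, describes a growth model for the 6- and 12-month data. It raises the possibility that arms differ at 12 weeks but that "these differences do not continue to increase or are not maintained". It then says: "The hypothesis of decreasing gains for the TF-CBT condition would be tested by adding a quadratic component to the linear growth model". The term "would test whether there are decelerations in the rate of change in symptoms from baseline to the 12 month outcome".

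Two other parts of that section bear on the question. The 12-week comparison is a separate two-level model, and it is the primary test. The growth model may place its intercept at 12 months so as to model "the effects of condition on the level of symptoms at the final time point", together with the rate of change over the whole period. This is put in permissive terms (analyses may be expanded, the intercept could be placed there), and the one Level 1 growth equation written out is linear in time. Section 3C5a compares successive models by likelihood ratio tests and deviance but gives no rule for which fit supplies the reported effect.

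On timing, section 3C4d says "Guardian-child dyads randomized to TF-CBT begin the 12-week group protocol within 2 weeks" and "All dyads are assessed again at 12-14 weeks post-baseline, 6-months, and 12-months post baseline". On purpose, section 3C4a gives maintenance of gains as the reason for the 6- and 12-month visits. Section 3C6 says that TF-CBT is withheld from controls at 6 months so that lasting impact can be studied.

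**The concern.** An effect that stops growing and an effect that disappears are different findings, and one coefficient is assigned to both. Treatment finishes at about the second of four visits. An effect that builds up during treatment and then simply holds therefore rises and goes flat, which is already a curve when time runs from baseline. If a kept gain and a lost gain both produce curvature of the same sign, the term answers whether the effect levelled off and is silent on whether it lasted.

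At stake is the interpretation of the follow-up, the part of the design for which the control arm goes without TF-CBT for a year. A significant term under the label of decreasing gains could be read as loss when nothing was lost.

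**Working it through.** **The plan's own figure.** The only number attached to the quadratic test is the detectable slope effect of .29 at 80% power (section 3C5c). With (1.960 + 0.842) x sqrt(4/N x design effect):

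- N = 640, no clustering: 2.802 x sqrt(4/640) = .221
- N = 640, design effect 1.7: .221 x sqrt(1.7) = .289. A design effect of 1.7 arises from ICC .10 in both arms (1 + 7 x .10), or from ICC .20 in TF-CBT only (average of 2.4 and 1).
- N = 320, no clustering: .313

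The ICC and variance components behind .29 are not given, so it can be neither confirmed nor faulted. The point does not depend on it.

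**Inputs from the documents.** Visits at baseline, 12-14 weeks (taken as month 3), 6 and 12 months (3C4d); 320 per arm (3C2b); groups of 8, alpha .05, effects of .35 and .50 SD, ICC up to .15 (3C5c).

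**Assumed.** Two-sided test; complete data; visit correlation .4 to .6; a group effect constant after baseline; and the four effect profiles below. The term is read as condition by time-squared, the reading most favourable to the plan. Differences are coded so that positive means TF-CBT is better; on the symptom scale every sign reverses.

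**Step 1: weights.** Least squares on the arm differences at t = 0, 3, 6, 12 gives:

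- time-squared coefficient: .0177, -.0101, -.0202, .0126
- 12-month value, linear fit: -.200, .057, .314, .829
- 12-month value, quadratic fit: .027, -.073, .055, .991

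**Step 2: apply them, with the 12-week effect set to 1.** For example, the time-squared coefficient if kept is -.0101 - .0202 + .0126 = -.0177.

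| Profile at months 0, 3, 6, 12 | Time-squared | 12-month, linear | 12-month, quadratic | 12-month minus 12-week |
|---|---|---|---|---|
| Kept (0, 1, 1, 1) | -.0177 | 1.20 | .97 | 0 |
| Half lost (0, 1, .75, .5) | -.0189 | .71 | .46 | -.5 |
| Fully lost (0, 1, .5, 0) | -.0202 | .21 | -.05 | -1 |
| Gone by month 6 (0, 1, 0, 0) | -.0101 | .06 | -.07 | -1 |

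The time-squared sign never changes, and its size does not rank the outcomes: the fastest loss gives the smallest term. Placing the second visit anywhere from 2.8 to 3.7 months changes neither statement.

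**Step 3: rejection rates.** Variance = 2 w'Vw/320 + 7 x ICC x (w'g)²/320, where w holds the weights, V has unit variances and a common correlation, and g = (0, 1, 1, 1). Example for a kept effect of .35 SD, correlation .4, ICC 0: w'Vw = .000589, SE = sqrt(2 x .000589/320) = .00192, z = .35 x .0177/.00192 = 3.22, rejection 90%. With ICC .15, z = 2.85 and rejection is 81%.

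| Test | Kept | Half lost | Fully lost | Gone by month 6 |
|---|---|---|---|---|
| Time-squared | 81-100% | 86-100% | 90-100% | 37-90% |
| 12-month, quadratic fit | 94-100% | 39-84% | 5-6% | 6-8% |
| 12-month minus 12-week | 5% | 52-94% | 98-100% | 98-100% |

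Child-level variation in curvature, which section 3C5b anticipates, lowers the first row. Adding an assumed quadratic SD of .02, squared, to w'Vw gives 63-98% if kept, over ICC 0 to .15. An SD of .03 gives 49-87%.

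**Step 4: the direct contrast.** Its weights are (0, -1, 0, 1), so w'g = 0 and a constant group effect cancels. The variance is 4 x (1 - correlation)/320. For half loss of .35 SD at correlation .4: .175/.0866 = 2.02, power 52%. At .6, power is 70%. For .50 SD the figures are 82% and 94%. At correlation .2 with .35 SD: .175/.100 = 1.75, power 42%.

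**The case against.** Four points can be made for the plan.

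1. The time-squared term is a proper test of deceleration, which the section names, and of an effect that stops growing. On that reading a significant term at a plateau is the correct answer. This stands; only the clause about gains not being maintained is left unserved.
2. The plan names a 12-month effect. A reader might infer that the plan cannot detect a lost effect at all. The documents do not support that: from the quadratic fit, the 12-month test rejects in 94-100% of trials if gains are kept and 5-6% if they are fully lost. The estimate is also nearly unbiased (.97, .46 and -.05 for true values 1, .5 and 0), so set beside the 12-week estimate it shows partial loss in size. What is missing is a formal estimate of that change with a standard error.
3. The linear fit misreads the 12-month level and rejects in 11-30% of trials when the effect is fully lost. This would happen only if the evidence of curvature were ignored. If the likelihood ratio tests of section 3C5a decide the model, the quadratic would nearly always be kept under full loss when children do not vary in curvature. The remaining weakness is that no retention rule is stated.
4. A reader might infer that a trial with every gain kept would almost always be reported as showing decreasing gains. That needs both the loss reading of the label and no child-level variation in curvature. With such variation the rate is lower and depends on an assumed SD. The same-sign result does not depend on it.

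**Conclusion.** The concern holds in a limited form. The time-squared term cannot test whether the 12-week gain is maintained, because its sign is the same whether the gain is kept, partly lost or fully lost, and its size does not order these cases. This follows from the visit times and the end of treatment at about the second visit. It rests on the assumed profiles but not on the correlation or ICC; those affect only the rejection rates, which also assume complete data.

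No stated test gives a formal estimate of change since 12 weeks. The 12-week and 12-month effects are levels at single times, and the slope and time-squared terms run from baseline. The 12-month effect partly fills the gap when taken from the quadratic fit, but the plan makes it optional and writes out only a linear equation, which reads 1.20 for a true 1 and .21 for a true 0.

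This should be corrected because maintenance is a stated purpose of the follow-up visits. It affects the follow-up analysis only and leaves the primary comparison at 12 weeks untouched.

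**What to change.** For the follow-up analysis only:

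- Add the arm difference at 12 months minus the arm difference at 12 weeks as the maintenance estimate. One way is a model with visit as a category, Treatment x Visit terms, a child-level covariance and a random effect for TF-CBT group. Report it with the 6- and 12-month effects.
- Interpret it by its estimate and confidence interval. A non-significant result does not show maintenance, since power for half loss is only 52-94% in the cases above and 42% for .35 SD at a visit correlation of .2.
- If the growth curve is kept, describe the time-squared term as a test of curvature only, and state that the 12-month effect comes from the quadratic fit. Replacing the growth curve altogether is a matter of preference; the single contrast closes the gap.

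The cost is analysis-plan wording and a routine model, with no new data or visits. Compared with the linear fit, the 12-month standard error is 5.6% larger at correlation .4 and 3.6% larger at .6 (at .4: 1/sqrt(.6 x .829 + .4) = 1.056, where .829 is the sum of squared linear 12-month weights). Compared with the quadratic fit it is under 1% larger. These figures assume complete data and no clustering.

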TF-CBT is rapidly being adopted by countries with diverse cultures and beliefs regarding trauma exposure, death, loss, and childhood. TF-CBT is currently being used in TZ (see 3C1), Zambia, China, Norway, Cambodia, Indonesia, Germany, Norway, Singapore, and the Netherlands. The book by the developers¹⁰² has been translated into Dutch, German, and Mandarin, with translations into Japanese, Korean, and Polish underway. The web-based training for TF-CBT (<http://tfcbt.musc.edu>) and CTG (<http://ctg.musc.edu>) includes residents from over 70 countries. Our team receives regular requests for conducting training in other countries (e.g., South Korea, Northern Uganda, Japan). Given the high percentage of orphans in Sub-Saharan African, their high rates of CTG, PTS, and trauma exposure, it is critical to build evidence to guide the implementation of EBPs and TF-CBT, specifically. Our pilot study (see section 3C1) shows preliminary promising findings for TF-CBT used with orphaned youth in TZ, providing the foundation for the proposed RCT.

3B. Innovation

The proposed study is innovative in five ways: 1) it represents the first RCT of a mental health EBP for orphans with CTG in LAMICs; 2) it incorporates and builds on local experience and expertise developed during our pilot study, adding to the potential sustainability of the intervention (see 3C1); 3) the study examine both clinical (CTG, PTS, depression) and broader outcomes, including any improvement in child daily functioning as well as implementation factors (e.g., TF-CBT fidelity, supervisory relationship); 4) the RCT includes regions within two countries (TZ and KE) that allow for testing TF-CBT in urban and rural settings, with diverse political histories and usual care services and supports; and 5) as the TF-CBT model appears to have relevance in a wide range of cultural settings, and if found effective in this trial, it would be an excellent candidate for broader dissemination and implementation to improve outcomes for orphans in LAMICS internationally.

To our knowledge, we are among the first to include already trained lay counselors in the training of the subsequent generation of lay counselors, thereby taking a systematic step toward building local expertise and sustainability. According to the *Lancet* series, "flexibility and creativity [is] needed to diversify the workforce"⁶⁴

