We will test hypotheses through a standard approach to model-building, focusing on creating parsimonious explanatory models through progressive taxonomies as follows^{122,123}. An unconditional model (i.e. one without predictors) of the outcome will be fitted first, which allows specification of the random effects, which in turn provides an estimation of the amount of interdependence at each level of clustering. For longitudinal models including multiple time points (i.e. client outcomes from baseline to follow up assessments), an unconditional growth model will be fit to identify time trends and inter-individual variance in trends. We will next test the effects of the primary variable of interest (e.g., condition assignment, or therapist fidelity to treatment model) on the outcome in a conditional model (i.e., one with predictors). Finally, theoretically relevant covariates will be

added to determine the robustness of the main effects. Relative goodness-of-fit for each successive model will be evaluated using likelihood ratio tests and deviance statistics.

3C5b. Primary Analyses

Aim 1. Test the effectiveness of a group model of TF-CBT for orphaned youth in two East African countries, including any variation by child age and gender.

Hypothesis 1: Children in the TF-CBT condition will demonstrate greater reductions in symptoms and greater improvement in overall functioning and the child-guardian relationship.

These analyses focus on whether TF-CBT produces significant reductions in symptoms (i.e. CTG, PTS, depression, behavioral problems) or improvement in functioning, or the child-guardian relationship compared to UC. Hypotheses will be tested in two ways using MLM. First, we test whether the TF-CBT condition differs from the UC condition at 12-weeks (i.e., end of TF-CBT). This hypothesis will be tested with a simple 2-level MLM, predicting the observed outcome (by child or guardian report) at 12-weeks, while accounting for clustering of individuals within TF-CBT groups, for the TF-CBT condition. The general Level 1 equation, which models individual differences in symptoms at 12-weeks, would be as follows:

Level 1:	$Symptoms_{ig} = B_{0g} + B_{1g}PreSx + B_{2g}Cov + e_{ig}$
Level 2:	$B_{0g} = \pi_{00} + \pi_{01}Treatment + r_{00}$ $B_{1g} = \pi_{10} + r_{00}$ $B_{2g} = \pi_{20}$

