For example, where the outcome is the level of symptoms for a given client i in group g ; B_{0g} (the intercept) represents the average 12-weeks level of symptoms for all children in a given group g , B_{1g} is the effect of pre-treatment symptoms, B_{2g} is the effect of

child/guardian-level covariates (such as demographics: child age, gender), and e_{it} represents residual variance in the outcome for individual i in group g . If randomization was effective, the effects of pre-treatment symptoms may be ignored. The Level 2 equations represent how the coefficients at Level 1 are distributed across treatment groups. Both the intercept and the effects of pre-treatment symptoms (if needed) would be specified as random variables, which would allow their effects to differ across treatment groups. The level 2 equation would follow the general form of $B_{0g} = \pi_{00} + \pi_{01}Treatment + r_{00}$, which uses condition-level variables (such as assignment to TF-CBT or UC) to predict how effects differ. Thus the hypothesis that group-based TF-CBT produces significant improvements in symptoms over the UC condition would be tested by evaluating the significance of π_{01} above, which tests the effects of condition assignment on 12-week symptoms.

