These aims would be tested by adding country and rural or urban setting as predictors at Level 2. These analyses would test whether country or setting explain between-condition differences in treatment outcomes at

a specific time point, and for the growth models, whether they explain differences between conditions in the rate of change over time.

Aim 3. Examine the impact of implementation factors (e.g., TF-CBT fidelity, lay counselor-supervisor relationship, child/guardian attendance) on outcomes.

Analyses for Aim 3 will focus on how implementation variables (such as attendance, fidelity, provider knowledge) are related to outcomes at 12-14 weeks (end of TF-CBT) and at the follow-ups. These analyses will be restricted to those in the TF-CBT condition. These Aims are tested by expanding the models described in Aims 1 and 2, above, to include implementation variables at both the individual level (such as attendance) and the group level (TF-CBT fidelity). For example, MLM equations that look at implementation effects on post-treatment levels of symptoms could be:

Level 1:	$Symptoms_{ig} = B_{0g} + B_{1g}PreSx + B_{2g}Cov + B_{3g}Attendance + e_{ig}$
Level 2:	$B_{0g} = \pi_{00} + \pi_{01}Fidelity + r_0$ $B_{1g} = \pi_{30}$ $B_{2g} = \pi_{30}$ $B_{3g} = \pi_{30} + r_2$

These models test how attendance during treatment and fidelity of the treatment provider influence symptoms at 12-weeks and at follow-ups, treating the intercept and the effects of attendance as random effects, and the

effects of pre-treatment symptoms and covariates as fixed effects.

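### The Aim 2 analysis, and Aim 1's age and gender clause, contain no treatment-by-factor term, so they cannot show whether the TF-CBT effect differs by country, setting, age or gender

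*Combined protocol and SAP*

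**What the plan says.** Section 3C5b writes the 12-week model in two levels. Treatment appears once, in the Level 2 equation for the intercept (coefficient π01). The covariate coefficient is a constant, B2g = π20, and child age and gender are given as examples of those covariates. Only π01 is named as the treatment test. On baseline symptoms (PreSx) the plan adds: "If randomization was effective, the effects of pre-treatment symptoms may be ignored".

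The Aim 1 statement nevertheless covers effectiveness "including any variation by child age and gender".

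For Aim 2 the method is one sentence: "These aims would be tested by adding country and rural or urban setting as predictors at Level 2". The stated purpose follows: "These analyses would test whether country or setting explain between-condition differences in treatment outcomes at" a given time point and, for the growth models, "whether they explain differences between conditions in the rate of change over time".

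The growth model is described as "allowing us to model the effects of condition on the level of symptoms at the final time point, and on the rate of change"; no treatment-by-factor term is named there. Section 3C5a says that covariates are added last, to check that the main effects are robust. Section 3C5c gives no power for any interaction.

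**The concern.** A question about whether country or setting accounts for the difference between arms is a question about effect modification. It needs a product of treatment with the factor. A main effect of country answers something else: whether symptom levels differ between Kenya and Tanzania, averaged in some way over the arms.

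The question matters to this trial. Section 3B lists as an innovation that the two regions "allow for testing TF-CBT in urban and rural settings, with diverse political histories and usual care services and supports". Section 3C3c gives reasons to expect a level difference and a comparator difference. In the earlier orphan cohort, Kenyan children had higher emotional and behavioral needs, and 31% of Kenyan against 15% of Tanzanian respondents reported counseling or emotional support at 36 months. Those figures come from another cohort, and the section adds that the high Kenyan support level was, anecdotally, not sustained. If only levels differ, a significant country term could still be reported as TF-CBT working differently in the two countries. Conversely, a real difference in effect could be missed.

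**Working it through.** **1. Structure.** With the Aim 2 predictors added, the 12-week model is

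E[Y] = π00 + π01·Treatment + π02·Country + π03·Setting + baseline symptoms + age and gender.

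The TF-CBT effect is π01 in both countries, both settings, both sexes and all ages. No coefficient measures a difference in effect.

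**2. Could the added terms explain away the treatment difference?** Table 2 plans 80 dyads in every country × setting × arm cell, so country and setting are orthogonal to treatment. With complete data and no baseline covariate, the treatment estimate is identical before and after (−0.407008 both times in one simulated data set). With baseline symptoms kept, it moves by at most .001 SD on average, and by .002 to .003 SD with 10% to 30% random loss.

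**3. Inputs for the sizes.** From the documents: 80 per cell (Table 2); 20 TF-CBT groups per region (3C2); 8 children per group, type I error .05, ICC values .06, .15 and .30, and an effect of .35 (3C5c). Section 3C5c discusses ICCs for providers; here they are applied to groups. Assumed: outcome SD 1, independent usual-care children, two-sided tests, ICC treated as known, pre-post correlation r (0 means baseline symptoms dropped), and the size of the country gap.

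Variance of the arm means:
- TF-CBT: V_T = [ICC + (1 − ICC − r²)/8]/40
- Usual care: V_U = (1 − r²)/320

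**4. The nearest figure in the plan.** Section 3C5c claims .80 power for a .35 main effect at ICC up to .15, quoting 320 children in total. With 320 per arm, SE = √(.00641 + .00313) = .098 and power is 95%; with 160 per arm it is 72%. Neither gives .80 exactly, but nothing below depends on that figure.

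**5. Precision of a treatment-by-country (or setting) term.** SE = 2√(V_T + V_U); difference detectable with 80% power = 2.80 × SE. With r = 0 and no dropout:

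| ICC | V_T | V_U | SE | Detectable (SD) | Power for .35 SD |
|---|---|---|---|---|---|
| 0 | .00313 | .00313 | .158 | .44 | 60% |
| .06 | .00444 | .00313 | .174 | .49 | 52% |
| .15 | .00641 | .00313 | .195 | .55 | 43% |
| .30 | .00969 | .00313 | .226 | .63 | 34% |

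Keeping baseline symptoms at ICC .06 gives SE .167, .155, .134 at r = .3, .5, .7, and power 55%, 62%, 74%. For age and gender the SE is the same if groups are single-sex and age-divided, as the feasibility focus groups advised (3C1b). If groups are mixed it is .146 to .158 without baseline symptoms.

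**6. What the country main effect picks up.** Under generalised least squares (GLS) its SE is 2√[V_T·V_U/(V_T + V_U)]. Its expected value is gap × (1 − r) + w × (difference in TF-CBT effect), with w = V_U/(V_T + V_U). Equal TF-CBT effects, ICC .06:

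| r | Country SE | Expected value, .30 gap | Significant at gap .10 / .20 / .30 SD |
|---|---|---|---|
| 0 (dropped) | .086 | .30 | 21% / 65% / 94% |
| .3 | .082 | .21 | 14% / 40% / 72% |
| .5 | .076 | .15 | 10% / 26% / 51% |
| .7 | .064 | .09 | 8% / 15% / 29% |

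The interaction is significant in about 5% throughout. Over ICC 0 to .30, the .30 gap gives 80% to 61%, 59% to 41% and 36% to 23% at r = .3, .5 and .7. A simulation (1,500 trials per case, ICC .06, baseline symptoms kept, .30 gap) gave 72%, 49% and 30% for the country term and 5% for the interaction.

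**7. The reverse case.** With no gap but a .35 SD difference in effect, w = .41, .39, .35 at r = .3, .5, .7, so the country coefficient is expected to be .14, .14, .12. A .30 gap with equal effects gives .21, .15, .09, so its size does not tell the two situations apart. With effects of .60 and .10, an offsetting level gap of .25 SD, ICC .15 and equal weighting of the arms, the country term was significant in 5% of 4,000 simulated trials and the interaction in 73%.

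**The case against.** The plan never says in so many words that it tests whether the TF-CBT effect differs. Aim 2's heading asks about differences in outcomes by country or setting, and main effects answer that. The equations are offered as general forms. In the growth model, covariates predict the time slope and condition is modelled at the level above, which could accommodate a condition-by-age-by-time term. Part 6 gives the chance of detecting a country difference that really exists, so it is harmful only if misread. The assumed gap has no basis in this trial, which enrols only children above a grief or stress threshold (3C4d).

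Much of this stands as a limit on scope. Main effects do serve the heading, and the rates in part 6 are not error rates of the country test itself. The precision figures may also be optimistic: 9 counselors per country are shared across 20 groups (3C3b), while the calculation treats groups as independent. But the general form never supplies the product terms, the only stated method for Aim 2 is main effects, and the balance of Table 2 removes the alternative reading that country explains away the treatment difference.

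**Conclusion.** The concern holds. The stated analysis cannot do what section 3C5b says it does for country and setting, and nothing in it addresses variation in effectiveness by age and gender. The structural point needs no assumed numbers; the sizes of the country-term rates depend on the assumed gap, correlation and ICC and are illustrations only. How far the country coefficient mixes level and effect differences also depends on the estimator, which the plan does not fix. Keeping baseline symptoms reduces the confusion when the gap is already present at baseline, but does not turn the country term into a test of effect modification.

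Not affected are the primary test of π01 and plain comparisons of outcome level, usual care received and implementation between countries and settings. This should be corrected before analysis, but it does not threaten the main result.

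**What to change.** In section 3C5b, add Treatment × Country and Treatment × Setting to the Level 2 intercept equation, add Treatment as a predictor of the age and gender coefficients, and write the matching products with time in the growth model. Keep baseline symptoms in the 12-week model for these analyses. Base any statement that the TF-CBT effect differs on these terms, reported as exploratory estimates with 95% confidence intervals and with their expected precision stated. Retain the country and setting main effects for outcome level, receipt of usual care and implementation outcomes, and say that this is the question they answer.

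The cost is wording and a few model terms, with no new data. The downside is that the modest power of the interaction tests becomes visible.
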